#### *FSD case/severe physical disease differences:*

To compare the odds of having received sickness benefit, unemployment benefit, or social assistance, between FSD cases and individuals with severe physical disease, logistic regression analyses will be performed with welfare benefit variables merged into a dichotomous dependent variable with two levels (0 = number of weeks < the median number in the total sample (reference), 1 = number of weeks  $\geq$  the median value in the total sample) and a dichotomous primary independent variable with two levels (0 = severe physical disease (reference) and 1 = FSD). Odds ratio with 95% CI will be used as measure of association.

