### **Objective**

To estimate the number of weeks of welfare benefits, i.e. sickness benefit, unemployment benefit and social assistance, for individuals with FSD and compare them to individuals without FSD and individuals with severe physical disease.

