### **Data**

Data from the DanFunD baseline cohort will be included (11); individuals with FSD are identified by means of self-reported questionnaires (n=9,656) (2) and diagnostic research interviews (n=1,590) (12). Individuals with severe physical disease are identified by self-reported questionnaires.

---

 Given the circumstances that interview-data are uploaded in Statistics Denmark

*Dependent variable:*

Data on welfare benefits will be obtained from The Danish Register for Evaluation of Marginalization (DREAM) which contains data on Danish citizens who have received social benefits or other welfare payments (13). Welfare benefit will be counted as number of weeks per year in a 10-year period before and 5-year period after the day the participant participated in the DanFunD baseline investigation.

Welfare benefits will be grouped into 7 categories where categories 1-3 are the main categories for investigation and categories 4-7 are used in order to exclude weeks of no transfer income/self-support, public retirement pension, emigration, and death (Table 1).

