**TABLE 1**

Category	Explanation	Coding in DREAM (Danish)
1) Sickness benefit	Individuals who receive sickness benefits such as employed citizens being ill, unemployed citizens currently ill, citizens in activation programs currently ill, and citizens in flexible jobs but currently ill	Ledighedsydelse (740, 743-748) Revalidering (760, 763-768) Fleksjob (771) Fleksjob, Sygedagpenge under fleksjob (774) Ressourceforløb (810, 813-818) Jobafklaring (870, 873-878) Sygedagpenge (890, 893-899)
2) Unemployment benefits	Unemployed citizens who receive unemployment benefit (full or part time, during vacation or activation) together with citizens on social assistance who are deemed ready-to-work, only receiving social assistance because of unemployment, but having no entitlement to unemployment benefit.	Dagpenge, ledighed (111) Supplerende dagpenge, ledighed (115) Kontanthjælp, jobparate (130, 133-139) Uddannelseshjælp, åbenlyst uddannelsesparat (140, 143-149) Uddannelseshjælp (720, 723-729) Kontanthjælp (730, 733-739)
3) Social assistance	A welfare payment administered by the municipal social service department and is allocated if citizens are unable to support themselves.	Skånejob (781) Førtidspension (783)
4) No transfer income/self-support	Individuals that do not receive welfare payments under the circumstances of sickness, unemployment, or social benefits. Including leave-of-absence schemes and grants from State Education Fund.	Voksenlærlinge (521) Efterløn (621) SU med ydelse (651) SU uden ydelse (652) Voksen uddannelsesstøtte og staten voksen uddannelsesstøtte (661) Barseldagpenge (881)

5) Public retirement pension	Folkepension (998)
6) Emigration	Ikke bosiddende i Danmark (997)
7) Death	Død (999)

*Independent variables:*

Participants with FSD will be defined as follows:

- FSD operationalised by the Bodily Distress Syndrome single- and multi-organ type will be defined with both self-reported questionnaires (14) and diagnostic interviews (3)
- Three functional somatic syndromes, i.e. irritable bowel (15), chronic widespread pain (16), and chronic fatigue (17) will be defined with questionnaires

Severe physical disease will be defined as having received at least one of the following five diagnoses: Cancer, stroke, myocardial infarction, other heart disease, and obstructive pulmonary disease.

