**Analytical plan**

Analyses will be conducted by Stata Statistical Software, version 17 (18). Separate analyses for each time period (10 years before and 3 years after the DanFunD baseline investigation) will be conducted.

*FSD case/FSD non-case descriptives:*

Percentages of participants having received at least one week of welfare benefits during the 10-year period before baseline and the 5-year period after baseline will be calculated for each FSD definition and displayed in figures (see example in Figure 1).

 Given the circumstances that interview-data are uploaded in Statistics Denmark

[figure not shown]

Figure 1

*FSD case/FSD non-case differences:*

To compare the mean number of weeks receiving sickness benefit, unemployment benefit, and social assistance, respectively, between cases and non-cases of FSD, linear regression analyses on each of the three main welfare variables will be performed with welfare benefit variables as the continuous dependent variable and the dichotomous FSD case-status variables as the primary independent variable.  $\beta$ -coefficients with 95% confidence intervals (CI) will be used as measure of association, and all analyses will be adjusted for sex and age. Linearity of age will be checked by expanding the model with natural cubic splines with five knots at the 5th, 27.5th, 50th, 72.5th, and 95th percentiles according to the recommendations by Harrell (19). Deviations from linearity will be tested using a  $\chi^2$ -test ( $p < 0.05$ ). To account for the possible positive skew and outliers in the welfare variables, optimally non-parametric bootstrap resampling with 100,000 repetitions will be performed. Significance will be judged from 95% bootstrapped CI of differences not overlapping with 0. If the assumptions for performing non-parametric bootstrap resampling are not fulfilled, generalized linear models will be used instead.

To compare the odds of having received at least one week of sickness benefit, unemployment benefit, or social assistance, between cases and non-cases of FSD, logistic regression analyses will be performed with welfare benefit variables as the dichotomous dependent variable and the dichotomous FSD case-status variables as the primary independent variable. Odds ratio with 95% CI will be used as measure of association.

*FSD case/severe physical disease descriptives:*

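### The objective is stated in weeks, but the comparison with severe physical disease gives no weeks and no difference in weeks

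*SAP*

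**What the plan says.** The SAP's Objective is "To estimate the number of weeks of welfare benefits", names three benefits, and goes on to "compare them to individuals without FSD and individuals with severe physical disease". The Data section adds that "categories 1-3 are the main categories for investigation", that is, sickness benefit, unemployment benefit and social assistance.

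Under FSD case/FSD non-case differences, the Analytical plan has a model for weeks. Its purpose is "To compare the mean number of weeks receiving sickness benefit, unemployment benefit, and social assistance, respectively, between cases and non-cases of FSD", and "linear regression analyses on each of the three main welfare variables will be performed", reported as β-coefficients with 95% CIs, adjusted for sex and age, and bootstrapped. If the bootstrap assumptions fail, "generalized linear models will be used instead". A separate logistic model there uses receipt of at least one week as its outcome.

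For severe physical disease, the descriptives section plans percentages with at least one week in two non-overlapping groups: FSD without severe disease, and severe disease without FSD. The differences section announces a comparison of the odds of having received benefit. Its outcome is "welfare benefit variables merged into a dichotomous dependent variable with two levels", where 1 means weeks at or above the total-sample median, and its only effect measure is an odds ratio with 95% CI.

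**The concern.** The Objective puts both comparators on the same footing and asks for weeks. The analysis delivers weeks for one of them. Followed as written, the report would state no mean number of weeks in the severe-disease group and no size of difference between it and the FSD group.

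Two features of the logistic model add to this. First, its label and its outcome disagree: odds of receipt means a cut at one week, whereas the cut is the median. Second, *merged* is not defined. If it pools the three benefits, the categories that the Data section calls the main ones are lost in this comparison. If it reduces each benefit to two levels, they are kept. Two analysts could build different outcomes from the same sentence.

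**Working it through.** **Text side by side**

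| | Versus no FSD | Versus severe physical disease |
|---|---|---|
| Objective | weeks, three benefits | weeks, three benefits |
| Any-benefit percentages | yes | yes |
| Mean weeks and difference | linear regression per benefit | none |
| Logistic outcome | at least one week | at or above the total-sample median |

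The only number of weeks in the right-hand column is the cut point itself. This holds under either reading of *merged*. The plan has no figure of its own to reproduce here.

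**Can the odds ratio stand in for weeks?** The SAP gives no distribution of weeks, so every input below is assumed. The figures are totals over a whole period, although the Data section counts weeks per year. They show what is possible, not what is likely.

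Let s be the share of a group at or above the cut, A the mean weeks among them and b the mean weeks below the cut. Then group mean = s × A + (1 − s) × b. Assume a total sample with 40% zeros and a median of 8 weeks, and b = 0.8 in both groups.

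*Unequal shares.* FSD: s = 0.6, A = 50. Severe disease: s = 0.5.
- Odds ratio = (0.6/0.4)/(0.5/0.5) = 1.50, whatever A is.
- FSD mean = 0.6 × 50 + 0.4 × 0.8 = 30.32.

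| A in severe disease | Mean in severe disease | FSD minus severe disease |
|---|---|---|
| 50 | 25.4 | +4.92 |
| 60 | 30.4 | −0.08 |
| 75 | 37.9 | −7.58 |
| 100 | 50.4 | −20.08 |

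*Equal shares.* With s = 0.5 in both groups the odds ratio is 1.00 and the FSD mean is 25.4. The same four values of A in severe disease give differences of 0, −5.0, −12.5 and −25.0.

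*Break-even.* The sign changes when A in severe disease exceeds (s₁ × 50 + (1 − s₁) × 0.8 − 0.5 × 0.8)/0.5, where s₁ is the FSD share.
- s₁ = 0.55, OR 1.22: 54.92, a ratio of 1.10 to the FSD value of 50.
- s₁ = 0.60, OR 1.50: 59.84, ratio 1.20.
- s₁ = 0.70, OR 2.33: 69.68, ratio 1.39.

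*Cross-check with the cut at one week.* Suppose 60% of FSD and 50% of severe disease have any weeks, so that OR = 1.50. With means among recipients of 40 and 40, 80 and 40, or 40 and 80, the differences are 24 − 20 = +4, 48 − 20 = +28 and 24 − 40 = −16. So correcting the cut alone does not supply weeks; the weeks model is needed as well.

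**Median of zero.** If more than half of the total sample has 0 weeks on the chosen outcome, the median is 0, everyone satisfies weeks ≥ 0 and is coded 1, and the model cannot be fitted. The SAP has no rule for that case.

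**The case against.** The best defence is that the Objective says compare and does not promise a mean difference for each comparator, and that a median split does compare the groups on weeks. That stands. A reader might infer that the severe-disease comparison is missing altogether; it is not. What is missing is its size, on the scale the Objective names.

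A second defence is that weeks are skewed and a split is robust. But the SAP anticipates skew in the non-case comparison and handles it with the bootstrap or a generalized linear model. It gives no reason for dropping that approach here.

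Third, *merged* may simply mean collapsing each variable to two levels, since the earlier logistic paragraph is worded much the same way. That is plausible. Loss of the main categories follows only from the pooled reading, and one clarifying phrase would settle it.

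Fourth, any dichotomised outcome can hide a reversal in means, and nothing in the documents suggests that these groups differ in that way. This also stands: the illustration shows that the odds ratio cannot stand in for weeks, not that it will mislead.

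Finally, a reader might infer that the median split will fail because most people have no benefit. The documents give no share with zero weeks. Nor can the share in one period be bounded from the other: the cohort ages between periods, and weeks of retirement pension, emigration and death are excluded.

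**Conclusion.** The point holds on the text alone. The SAP sets an objective in weeks against two comparators and plans a weeks estimate against only one. For severe physical disease it gives a coarse contrast whose label does not match its outcome, unless the median is 1 week, and whose outcome can be built in two ways.

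On the assumed whole-period totals, an odds ratio of 1.50 is compatible with differences from about +5 to −20 weeks. Over a 10-year period that is about +0.5 to −2.0 weeks per year. The odds ratio therefore does not fix the size of the difference, or necessarily its sign. The textual finding does not depend on these figures. The zero-median failure is conditional.

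This should be corrected before analysis. It does not touch the comparison with people without FSD, and the median split need not be deleted to close the gap.

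**What to change.** In the section on differences between FSD and severe physical disease:

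1. Add the weeks regression already specified for cases versus non-cases, for each of the three benefits and each time period, with bootstrapped CIs, in the non-overlapping groups of the descriptives section. State the sex and age adjustment explicitly; the earlier sentence on adjusting all analyses may already cover it. If the generalized linear model fallback is carried over, name its family and link, which the SAP does not do now.
2. Make the logistic outcome match its label: at least one week, one model per benefit.
3. If the median split is kept as a secondary analysis, relabel it as weeks at or above the median, state that it is one model per benefit, and give a rule for a median of 0.
4. First reconcile the length of follow-up. The Analytical plan opens with 3 years after baseline and then uses 5 years, as does the Data section, so each time period is not yet defined.

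**Cost.** The change needs SAP wording plus runs on data and methods already planned. New linear models: 3 benefits × 2 periods × 4, 5 or 7 FSD definitions = 24, 30 or 42. The count depends on how the "single- and multi-organ type" of Bodily Distress Syndrome is counted and on whether interview data are available. With 100,000 repetitions each, that is 2.4 to 4.2 million small regressions. If *merged* means pooled, the per-benefit logistic models (24 to 42) replace 2 × 4 to 2 × 7 = 8 to 14; otherwise their number does not change.

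The downside is more results to report in a plan that states no multiplicity control. If every null were true, 0.05 × 24 = 1.2 to 0.05 × 42 = 2.1 of the new linear results would be expected to exclude 0 by chance.

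If the sponsor does not want weeks for this comparator, the Objective should say so. That costs only wording, but items 2 to 4 still apply.

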Percentages of participants receiving at least one week of welfare benefits during the 10-year period before baseline and the 5-year period after baseline will be calculated for individuals with FSD (and no severe physical disease) and individuals with severe physical disease (and no FSD) and displayed in figures (see example in Figure 1).

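### The FSD versus severe physical disease analysis announces receipt of benefit but codes weeks at or above the sample median, a rule that yields no odds ratio if the median is zero

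*SAP*

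**What the plan says.** In the SAP section *FSD case/severe physical disease differences*, the aim is "To compare the odds of having received sickness benefit, unemployment benefit, or social assistance, between FSD cases and individuals with severe physical disease". The outcome is built from "welfare benefit variables merged into a dichotomous dependent variable with two levels", coded "0 = number of weeks < the median number in the total sample (reference), 1 = number of weeks" at or above "the median value in the total sample". The effect measure is an odds ratio with a 95% CI.

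Three other places bear on this:

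- The *Objective* is about quantity: "To estimate the number of weeks of welfare benefits, i.e. sickness benefit, unemployment benefit and social assistance, for individuals with FSD", compared with people without FSD and with people with severe physical disease.
- In *FSD case/FSD non-case differences*, the logistic model compares the "odds of having received at least one week of sickness benefit, unemployment benefit, or social assistance". There, receipt means one week or more.
- In *FSD case/severe physical disease descriptives*, the same two groups are described by "Percentages of participants receiving at least one week of welfare benefits during the 10-year period before baseline and the 5-year period after baseline".

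The *Analytical plan* also specifies "Separate analyses for each time period", so the coding rule has to work in the window before baseline and in the window after it.

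**The concern.** There are three linked faults.

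1. **Aim and coding differ.** The section announces receipt but codes a median split on weeks. These are generally different outcomes. The odds ratio would not correspond to the percentages displayed for the same two groups, which are based on one week or more.
2. **The rule can collapse to one level.** Weeks cannot be negative. If the median is 0, nobody lies below it, everyone is coded 1 and the logistic model has nothing to estimate. The SAP gives no fallback here, although it does give one for the bootstrap analysis.
3. **The sample that supplies the median is not defined.** It could be the whole cohort or only the two groups being compared, and the choice can move the cut-point.

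This is the only inferential analysis planned for FSD against severe physical disease. If the median is 0, a new cut-point would have to be chosen after the data have been seen. If the median is above one week, the result is introduced as receipt but measures higher use.

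**Working it through.** **Inputs.** The SAP's *Data* section gives n = 9,656 with questionnaire data and n = 1,590 with interviews, and counts benefit in weeks, so the minimum is 0. The coding rule is as quoted. The SAP states no receipt share, median or group size for this comparison, so there is no figure of its own to reproduce. Receipt shares below are assumptions and are shown over a range.

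**Step 1: when the median is 0.** For even n, the median is the mean of the two middle ordered values. With R recipients there are n − R zeros, and the median is 0 exactly when n − R ≥ n/2 + 1, that is R ≤ n/2 − 1.

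- n = 9,656: R ≤ 4,828 − 1 = 4,827.
- n = 1,590: R ≤ 795 − 1 = 794.

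**Step 2: what the rule then does.**

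| n | Recipients | Median | Coded 1 / 0 with ≥ median | Coded 1 / 0 with > median |
|---|---|---|---|---|
| 9,656 | 3,862 (assumed 40%) | 0 | 9,656 / 0 | 3,862 / 5,794 |
| 9,656 | 4,827 | 0 | 9,656 / 0 | 4,827 / 4,829 |
| 9,656 | 4,828 | above 0 | 4,828 / 4,828 | 4,828 / 4,828 |
| 1,590 | 636 (assumed 40%) | 0 | 1,590 / 0 | 636 / 954 |
| 1,590 | 794 | 0 | 1,590 / 0 | 794 / 796 |

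When the median is 0, every person in any subset is also coded 1, so restricting the model to the two compared groups does not help. Both groups then have nobody at level 0 and the odds ratio is 0/0. A logistic fit to an outcome that was 1 for all 500 simulated people did not converge and returned standard errors of 229 and 246. Averaging weeks per year over a window rescales the median but does not change the zero-median condition.

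**Step 3: what the rule does when the median is positive.** At most n/2 people lie below the median. All (1 − p)n non-recipients are among them, so at most n/2 − (1 − p)n = (p − 0.5)n recipients are coded 0. As a share of recipients this is at most (p − 0.5)/p:

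- p = 55%: 0.05/0.55 = 9.1%
- p = 60%: 0.10/0.60 = 16.7%
- p = 70%: 0.20/0.70 = 28.6%
- p = 90%: 0.40/0.90 = 44.4%

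Simulated weeks with assumed geometric and log-normal shapes came close to this bound without exceeding it: 5–7%, 11–15%, 27–28% and 42–44%. In a further run with n = 9,656 and an assumed exponential shape, 80% receipt gave a median of 20 weeks and only 50.6% coded 1. At 51% receipt the median was 1 week, and the rule coincided with receipt. The bound applies to the sample that supplies the median. It does not bound either compared group if the median comes from the whole cohort.

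**Step 4: pooled or separate benefits.** If the three benefits are pooled, receipt is higher and a zero median less likely. Assumed separate shares of 30%, 30% and 6%, if independent, give 1 − 0.70 × 0.70 × 0.94 = 54% with any benefit. Shares of 20%, 20% and 5% give 1 − 0.80 × 0.80 × 0.95 = 39%. The first is above one half and the second below it.

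**The case against.** The strongest reply is that the collapse is possible but not shown. The singular dependent variable reads most naturally as pooled benefits, SAP Table 1 makes that pool broad, and one window covers 10 years, so a positive median is quite plausible. If the collapse did occur it would be visible, because a constant outcome stops the model and cannot give a wrong estimate unnoticed. On the mismatch, the coding stands in the same sentence as the aim, so a careful reader can see what is being modelled. A median split may also be deliberate, since it keeps some information on weeks, which is what the objective concerns. Finally, the plain reading of the total sample is the full cohort.

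Much of this is fair as to likelihood. The documents cannot settle whether the median is 0, and using a different outcome from the FSD case/non-case model is not in itself an error. Two things remain. The stated aim and the stated coding still disagree, and nothing elsewhere in the SAP reconciles them. The two defences also pull against each other: the more people who received benefit, the safer the rule is from collapse, but the more recipients can be coded together with non-recipients.

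**Conclusion.** The point holds. The mismatch between the announced outcome and the coded one is certain from the text and disappears only if the median is above zero with no recipient below it. The collapse is exact but conditional: it occurs if fewer than half of the sample supplying the median received benefit, which is at most 4,827 of 9,656 if that sample is the questionnaire cohort. With a positive median, the share of recipients coded 0 in that sample is at most 9% to 44% over assumed receipt of 55% to 90%. All receipt shares are assumptions because the SAP gives none. The section should be corrected before the data are analysed, since it carries the only inferential comparison with severe physical disease.

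**What to change.** Make the aim and the coding agree, keeping a two-level outcome. Either of these would do:

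- **(a) A weeks-based outcome, in line with the objective.** Describe it as higher use. Code 1 for weeks above a cut in weeks fixed in advance, or strictly above the median of a defined sample. The strict inequality keeps two levels when the median is 0, but the outcome then becomes any receipt. Its meaning could therefore differ between the two time windows and would have to be reported as such. A fixed cut avoids that shift. The strict-median version also moves participants exactly at a positive median from 1 to 0.
- **(b) Receipt.** Code one week or more against none, as in the FSD case/non-case logistic model. This matches the descriptive percentages for the same groups but gives up the information on number of weeks in this comparison.

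In both cases, state whether the three benefits are pooled or analysed one by one. If a median is kept under (a), also state which sample supplies it and that it is taken separately in each time window.

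The cost is one or two sentences of SAP wording and no new data.
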